# Master Protocol

associated study number and participant identification number. The lead PI and Central Study Coordinator will review the Eligibility Screening Checklist. After review, the local investigator will be informed of eligibility status via a fax and/or e-mail within 24 hours, if received Monday through Thursday. If the form is received on Friday, eligibility will be confirmed by the next business day.

## **11.1.5 Study Enrollment**

Subjects may be enrolled on the study once all eligibility requirements for the study have been met and confirmed. **Subjects who sign informed consent for the protocol and undergo screening for eligibility should not be started on the study drug until the screening is completed and they are deemed to meet all eligibility criteria.** Study enrollment is accomplished by completing the Enrollment Form (Appendix D). The Enrollment Form will be completed and faxed to the Coordinating Center ([name]). The fax should be sent to the attention of the Central Study Coordinator and must include the associated study number and participant identification number.

## **11.1.6 Dose Assignment**

The dose will be assigned by the local PI and Study Coordinator at the time of study enrollment based on the subject's body surface area. The prescribed amount of leucine will be rounded up to the nearest dosage tablet as indicated in the Leucine Dosage Calculation Table (Appendix E). A Leucine Dose Assignment Form (Appendix F) will be faxed to the participating institution from the Coordinating Center.

## **11.2 IRB Approval**

Local IRB approval must be obtained at all participating sites in order to begin enrollment onto this protocol. Sites must submit copies of IRB approval to the Coordinating Center. IRB approval documents should be faxed to the Central Study Coordinator along with a cover sheet ([name] at [name]), e-mailed ([contact]) or mailed to the Coordinating Center.

## **11.3 Diamond Blackfan Anemia Registry (DBAR)**

The Diamond Blackfan Anemia Registry is a demographic, laboratory and clinical database of patients with DBA in North America. Subjects screened for this study may be offered enrollment in the DBAR (through a separate consent and questionnaire) by their local investigator(s). Enrollment in the DBAR is not required for participation in this study.

# **12.0 DATA COLLECTION (Appendices D and G)**

## **12.1 Enrollment Data (Appendix D)**

**12.1.1** Demographics required for shipping refills

**12.1.2** Sex, race, date of birth, date of diagnosis (if available) (birth date to be collected in order to reduce error of mistaking one subject for another with the same age and initials)

**12.1.3** Current and past medications

**12.1.4** Transfusion history

**12.1.5** Completion of DBAR consent and questionnaire – if the subject (or his/her parent/guardian) wants to enroll in the DBA Registry – which is not part of this protocol but will be offered to the subject under its own protocol/consent

# Master Protocol

## **12.2 Case Report Form Data (Appendix G)**

The Case Report Form data is to be collected at baseline, at Weeks 2 and 4 and at Months 2, 3, 4, 5, 6, 7, 8, and 9 (or at time of transfusion, except where indicated otherwise). Each visit can be +/- 1 week of the requested time except week 2. Blood drawings can also be +/- 1 week of the requested time except week 2.

### **12.2.1 Physical Examination**

**12.2.1.1** Temperature, Pulse and Blood Pressure

**12.2.1.2** Height (cm) at baseline, month 4 and month 9, weight (kg), and body surface area (M)

### **12.2.2 Laboratory Examinations**

**12.2.2.1** CBC with platelet count, differential, and red cell indices

**12.2.2.2** Reticulocyte count

**12.2.2.3** Percent Hemoglobin F at baseline and then every 3 months and at study completion

**12.2.2.4** Hepatic transaminases, serum bilirubin, creatinine, and blood urea nitrogen

**12.2.2.5** Serum ferritin at baseline and then every three months and at study completion

**12.2.2.6** If female and of child-bearing potential, pregnancy test at baseline and every 3 months

**12.2.2.7** Plasma leucine level as well as levels of isoleucine and valine and an amino acid profile at baseline. Plasma leucine levels are obtained for research only and will not be used for clinical decision making. This extra blood will be drawn at the same time as standard routine clinical blood draws. A standard 10cc's (2 teaspoons) will be taken as part of clinical care, with an additional 5 cc's (1 teaspoon) taken after Leucine treatment begins to monitor leucine levels in the blood. Plasma leucine levels (5 cc's) will also be drawn at 2 weeks, 4 weeks, then months 3, 6, and 9 months (These are the extra tests for this study protocol. All the others are standard of care for the enrolled subjects.) Subjects will fast for 4 hours and hold the morning dose of Leucine for evaluation of the Leucine level at these time points. Blood drawings can be  $\pm$  7 days of the requested time, except week 2.

Laboratory examinations 12.2.2.1, 12.2.2.2, 12.2.2.4 and 12.2.2.5 are standard of care for transfused DBA subjects who are on chelation medication – which the chronically transfused subjects eligible for this protocol will be receiving; 12.2.2.3, 12.2.2.6 and 12.2.2.7 are extra tests that are specific to the study protocol. The instructions for sample collection and shipping of blood for amino acid levels are delineated in Appendix H. The blood samples will be batched and shipped directly from the participating institution to Case Western Reserve University, Ohio where the tests will be performed. The costs for the mailing will be provided by the Coordinating Center through a FedEx account.

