## 6.7 Pregnancy/Lactation

Excessive leucine administration interferes with embryo development in rats. Scientific evidence for the safe use of branched chain amino acids during pregnancy and lactation is not available as there are no human data.

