## 9.0 PATIENT ELIGIBILITY

All clinical and laboratory studies to determine patient eligibility must be performed within 30 days prior to study enrollment unless otherwise indicated. Laboratory values used to assess eligibility must be no older than thirty days at the start of therapy. Laboratory tests need not be repeated if therapy starts within thirty days of obtaining labs to assess eligibility. If a post-enrollment lab value is outside the limits of eligibility, or laboratory values are >30 days old, then the following laboratory evaluations must be re-checked prior to initiating therapy: CBC with differential, bilirubin, ALT (SGPT) and serum creatinine. If the recheck is outside the limits of eligibility, the patient may not receive protocol therapy and will be considered off protocol.

**Important note:** The eligibility criteria listed below are interpreted literally and cannot be waived. All clinical and laboratory data required for determining eligibility of a subject enrolled on this trial must be available in the patient's medical or research record which will serve as the source document for verification at the time of audit.

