- Total Bilirubin  $\leq 1.5 \times$  upper limit of normal (ULN) for age, and
- SGPT (ALT)  $< 5 \times$  upper limit of normal (ULN) for age
- Serum albumin  $\geq 2$  g/dL

**9.1.5** Negative pregnancy test if subject is a menstruating female and documentation of agreement to use adequate contraception for at least 28 days before starting the study, while taking the leucine, and for at least 3 months after the last dose of study medication .

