## 13.3 Schedule of Evaluations

Oral Leucine x 9 months

VISIT *	0	2wk	4wk	2mo	3mo	4mo	5mo	6mo	7mo	8mo	9mo
PE **	X	X	X	X	X	X	X	X	X	X	X
BP	X	X	X	X	X	X	X	X	X	X	X
Height	X					X					X
Weight	X	X	X	X	X	X	X	X	X	X	X
CBC with Retic ***	X	X	X	X	X	X	X	X	X	X	X
%Hb F	X				X			X			X
Chemistry**** Panel	X	X	X	X	X	X	X	X	X	X	X
Ferritin	X				X			X			X
Pregnancy test	X				X			X			
Leucine level	X	X	X		X			X			X

\*Each visit can be  $\pm$  1 week of the requested time – except visit 2.

\*\* PE includes Temperature, Pulse and Blood Pressure complete physical exam as clinically necessary \*\*\* CBC to include WBC, RBC, Hb, Hct, Plts, differential and reticulocyte count (%)

\*\*\*\* Chemistry Panel to include Urea Nitrogen, Creatinine, AST, ALT, Bilirubin, total and direct,

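### Pregnancy testing: the schedule in 13.3 stops at month 6 where 12.2.2.6 most naturally runs to month 9, and, separately, the re-check list in 9.0 omits two laboratory eligibility criteria

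*Combined protocol and SAP*

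**What the plan says.** **Frequency in the text.** Section 12.2.2.6 reads: "If female and of child-bearing potential, pregnancy test at baseline and every 3 months". It names no last test. Two neighbouring items are worded slightly differently. Item 12.2.2.3 reads "Percent Hemoglobin F at baseline and then every 3 months and at study completion" and item 12.2.2.5 reads "Serum ferritin at baseline and then every three months and at study completion".

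**Frequency in the table.** In 13.3 the row "Pregnancy test" is marked at visits 0, 3 months and 6 months and is blank at 9 months. The haemoglobin F, ferritin and leucine rows are all marked at 9 months.

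**Length of exposure and follow-up.** Section 13.0 gives leucine for 9 months. Section 12.2 collects data at baseline and then "at Weeks 2 and 4 and at Months 2, 3, 4, 5, 6, 7, 8, and 9". Section 9.1.5 requires contraception before the start, then "while taking the leucine, and for at least 3 months after the last dose of study medication". No visit is scheduled after month 9.

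**Stated risk.** Section 6.7 says: "Excessive leucine administration interferes with embryo development in rats". It adds that there are no human data on safe use in pregnancy or lactation. Pregnancy is an exclusion (9.2.4).

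**Start of treatment.** Section 9.0 requires laboratory values used for eligibility to be at most 30 days old when therapy begins. If they are older, or if a value after enrolment falls outside the limits, the tests to repeat are "CBC with differential, bilirubin, ALT (SGPT) and serum creatinine". The pregnancy test (9.1.5) and serum albumin (9.1.4) are eligibility criteria and are not on that list.

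**The concern.** There are two separate inconsistencies.

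The first concerns the end of dosing. Sites usually work from the schedule table. A site that follows 13.3 would do its last pregnancy test at month 6, with 3 months of leucine still to come, while a site that follows 12.2.2.6 would probably test again at month 9. Sites could therefore differ, and under the table the end of exposure has no scheduled check for a risk that the protocol itself names. Safety is one of the primary objectives (4.1.3).

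The second concerns the start of dosing. The general rule in 9.0 and the list that puts it into practice do not cover the same tests. A site that works from the list alone could begin leucine on a pregnancy test or an albumin value more than 30 days old and still believe it had complied.

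**Working it through.** No sample size, power or error rate is involved. The check sets the sections side by side and counts months.

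**Inputs**
- Tests marked in 13.3: months 0, 3 and 6.
- Interval in 12.2.2.6: every 3 months from baseline.
- Dosing: 9 months (13.0).
- Contraception after the last dose: at least 3 months (9.1.5), so the period from first dose to the end of required contraception is 9 + 3 = 12 months at the minimum.

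**Step 1. Does the table follow from the text?**

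| Reading of 12.2.2.6 | Test months | Number of tests | Matches 13.3? |
|---|---|---|---|
| Every 3 months through the month 9 visit | 0, 3, 6, 9 | 4 | No |
| Every 3 months, without a test at completion | 0, 3, 6 | 3 | Yes |

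The first reading is the more natural. The text sets no end before month 9, and there is a visit at month 9. Section 12.4 points the same way: it has forms submitted at 3-monthly intervals, counts completion among them, and gives the total as three, which fits months 3, 6 and 9. The protocol there treats completion as one of the 3-monthly points.

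**Step 2. Time with no later scheduled test, under 13.3 as it stands**
- Within dosing: (9 − 6) / 9 = 3/9 = 33%.
- From first dose to the end of required contraception: (12 − 6) / 12 = 6/12 = 50%.

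**Step 3. The same, with a test at month 9**
- Within dosing: (9 − 9) / 9 = 0/9 = 0%.
- From first dose to the end of required contraception: (12 − 9) / 12 = 3/12 = 25%.

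The month 9 test closes the gap within dosing. The 3 months after the last dose stay uncovered, because nothing is scheduled then.

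**Step 4. The re-check list against the laboratory eligibility criteria**

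| Test | Eligibility criterion in 9.1? | On the 9.0 re-check list? |
|---|---|---|
| Bilirubin | Yes (9.1.4) | Yes |
| ALT | Yes (9.1.4) | Yes |
| Albumin | Yes (9.1.4) | No |
| Creatinine | Yes (9.1.3) | Yes |
| Pregnancy test | Yes (9.1.5) | No |
| CBC with differential | No limit set in 9.1 | Yes |

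Two criteria are missing from the list, and one listed test has no limit against which a repeat could fail.

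**Step 5. Reporting.** The SAE definitions in 18.4 and the reporting text in 18.1 do not name pregnancy. Section 18.4.8 keeps SAE reporting open for 12 weeks after participation stops, which is close to the contraception period, but an uncomplicated pregnancy does not clearly meet any of the listed criteria.

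**The case against.** **Text and table may agree.** The haemoglobin F and ferritin items add a test at study completion, and the pregnancy item does not. On that wording, tests at 0, 3 and 6 months fit both places. This stands as a possible reading, so a reader who infers a flat self-contradiction goes too far. It is a probable mismatch. The wording of 12.4 still favours month 9, and sites need one answer in either case.

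**The general 30-day rule already covers the start.** It applies to every laboratory value used for eligibility, the re-check list is conditional, and a pregnancy test is scheduled at visit 0. This largely stands and makes the second point narrow. Nor do the documents show that a start more than 30 days after the test is likely: eligibility is confirmed within a day or by the next business day (11.1), and no shipping time is given. The rule and its list still do not match.

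**Pregnancies would not simply be missed.** A reader might infer that conceptions late in dosing or afterwards would go undetected and that the safety results would show none. The documents do not support that. Visits continue monthly to month 9 with adverse events collected, SAEs are reported for 12 weeks afterwards, and unanticipated problems go to the research monitor (17.2). What is missing is a scheduled test.

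**The two points are unconnected.** A reader might link the re-check list to late conceptions. It concerns only the start of dosing and has no bearing on them.

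**The affected group is small and of unknown size.** At most 50 subjects are enrolled, from age 2, and most are expected to be children. The percentages count calendar months, not people at risk. This stands.

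**Conclusion.** The point holds as two separate inconsistencies, both worth correcting.

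1. Section 12.2.2.6, on its natural reading, includes a month 9 pregnancy test that 13.3 does not mark. Under the table, 3 of 9 dosing months (33%) are followed by no scheduled test. Counting to the end of required contraception, the figure is 6 of 12 months (50%), half of which lies after the last dose.
2. The re-check list in 9.0 omits two laboratory eligibility criteria, the pregnancy test and albumin, and so does not match the 30-day rule in the same section.

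These conclusions assume 9 full months of dosing, the minimum 3-month contraception period, and the schedule row as it appears in the protocol.

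The animal finding in 6.7 refers to excessive administration. The documents do not say that it applies at the study dose, and they do not state that it is the reason for the contraception requirement. The lack of a named reporting route for pregnancy is a secondary clarification: the case report form, SAE form and consent appendices are not in the text available for review, so one may exist there. No endpoint, estimate or statistical figure is affected.

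**What to change.** - **Sections 12.2.2.6 and 13.3:** reconcile them on the month 9 pregnancy test. On the plain reading of 12.2.2.6 this means marking the test at month 9 in 13.3. If no test at completion is intended, 12.2.2.6 should say so.
- **Section 9.0:** align the re-check list with the laboratory eligibility criteria in 9.1 and with the general 30-day rule, so that the pregnancy test and albumin are covered. Either say what limit a repeated CBC is judged against or explain why it is listed.
- **Section 18:** if the appendices do not already do so, state how a pregnancy during dosing or in the 3 months after the last dose is reported and how its outcome is recorded. A month 9 test does not cover that later period.

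The cost is one more pregnancy test per eligible female, at a visit where blood is already drawn, an occasional repeat before dosing, and a few lines of amendment text.

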### **12.2.3 Other Specifics**

**12.3.3.1** Transfusion history (date and amount in ml and/or units q 3-4 weeks based on transfusions)

**12.3.3.2** Adverse side effects

**12.3.3.3** Hospitalizations (cause, dates)

## **12.4 Data Submission**

# Master Protocol

Case Report Forms (Appendix G) will be completed by the local PI and/or his/her designee at each subject visit. Case Report forms will be faxed to the Coordinating Center ([name]) where data will be stored on a secure database. These forms will be required to be submitted every 3 months, including at study completion (three times in total). The central Study Coordinator will perform data integrity monitoring visits of a minimum of 20% of the entered data through cross-checking and source documentation. Data will be analyzed with biostatistical support after completion of the study.

## 12.5 Data Storage

An institution or, when appropriate, an IRB shall prepare and maintain adequate documentation of IRB activities, including the following:

- (1) Copies of all research proposals reviewed; scientific evaluations, if any, that accompany the proposals; approved sample consent documents; progress reports submitted by investigators; and reports of injuries to subjects.
- (2) Copies of all correspondence between the IRB and the investigators.

With regard to the consent document, all sites must specify consent document storage and length of time, as well as destroyed/disposed specifics. Also research records and data storage and time destroyed/disposed, hard copies vs. electronic storage, research specimens storage and time destroyed/disposed, and any special storage conditions must be specified according to federal and institutional requirements.

Electronic and paper clinical research records will be retained for at least 7 years for adult subjects and 10 years for pediatric subjects after completion of the research study or at least 2 years after marketing approval by the FDA (or if not approved, until 2 years after shipment and delivery for investigational use is discontinued), whichever is longer. Electronic or paperless data sets should be kept on a secure server with adequate backup to assure record retention. Paper research records should be maintained in a secure office, in a secure file cabinet for the duration of the study and then archived.

All data collected from all health system sources will be maintained on a secure and password protected server and backed up every 24 hours. Study staff should have restricted access to directories and files on the server, according to project responsibilities. "Login/password security" should be used to control access to the network. Individuals with data entry permissions are able to add records only to the databases to which they have access.

A unique participant identification number will be assigned to each subject at the time of enrollment. In an effort to correlate information every unique PIN will be linked (coded) with the subject's medical record information. The coded link between this unique identifier and the subject's identifying information will be maintained in locked files. When information is shared internally or externally, investigators will only be provided with the subject's unique PIN.

Accurate and complete study records will be maintained and made available to representatives of the U.S. Army Medical Research and Materiel Command, the North Shore-LIJ Health System, and other federal and state authorities as a part of their responsibility to protect human subjects in

# Master Protocol

research. Research records will be stored in a confidential manner so as to protect the confidentiality of subject information.

## 13.0 STUDY DRUG ADMINISTRATION

Each subject will receive standard dose Leucine therapy for 9 months:

- 700 mg/m^2/dose orally three times daily for a total of 2100 mg/m^2/day

### 13.1 Study Drug - Leucine

This clinical trial will only utilize commercially available Leucine from Ajinomoto Aminoscience LLC, Raleigh, NC. The Leucine will be supplied in capsule form in 250 mg/capsule concentration. The Coordinating Center will purchase the Leucine supply.

**13.1.1 Dispensing of Study Drug** Once the subject has signed consent and is enrolled on the study, the local PI will be faxed the Dose Assignment Form from the Coordinating Center. The participating center will complete the Supply Request (Appendix F) and fax it to the Coordinating Center at [contact]. Once received the Coordinating Center's Study Pharmacy will be informed of the subject enrollment and will dispense a 3-month supply of the Leucine to the participating subject. The Leucine will be dispensed in 250 mg capsules, in child-proof capped containers, to be stored at room temperature. The shipment will be sent directly to the subject. Upon request, local investigators may dispense the study drug after showing they are able to store drug in a locked area and maintain a log of receiving and dispensing the study drug.

#### 13.1.2 Dispensing of Study Drug to Subject

The drug will be shipped directly to the subject from the coordinating site. The amount sent will be enough drug for a 3 month period.

#### 13.1.3 Medication Instructions

The Leucine Dose Assignment Form (Appendix F) will be faxed/e-mailed to the local PI to be reviewed with the subject. Instructions for medication usage will be distributed to the subject and/or parent/guardian of the subject along with the dose. May be taken with or without food. Capsules can be mixed into food or dissolved in liquids. Total daily dose will be divided into 3 doses to be given AM, afternoon and PM.

#### 13.1.4 Concomitant Medications

Concomitant medications will be documented on the Case Report Form (Appendix G).

## 13.2 Transfusion Therapy During Study Drug Administration

Subjects will receive 10-15 ml/kg/transfusion, with all volumes recorded on the Case Report Forms.

**13.2.1 If the hemoglobin (Hb) is less than 8 gm/dL and there is no evidence of reticulocyte response (retic count < 0.5%), the subject will be transfused as usual.**

**13.2.2 If the Hb is greater than 8 gm/dL, the reticulocyte count is greater than 0.5% (or baseline) and the subject is clinically stable (without fever, respiratory illness, etc.), the transfusion should be held.** The subject should be followed again in 1-2 weeks and reassessment will be made to see if a response is occurring.

**13.2.3 If the Hb is between 7-8 gm/dL, the reticulocyte count is greater than 0.5% (or baseline), and the subject is clinically stable, then the subject can opt out of transfusion, based upon clinical considerations, for one week, or receive 10 ml/kg packed red blood cell transfusion so as not to**

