# Master Protocol

**14.1.2 Partial Response (PR)** - Hb < 9 gm/dL with an increase in reticulocyte count to 1% and any transfusion interval increase

**14.1.3 No Response (NR)** - No change in transfusion needs, no change in Hb or reticulocyte count

**14.1.4 Progression** - An increased transfusion requirement with increased volume or increased interval

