### 16.2 Specific Statistical Aims of the Study (for the Data Analysis)

**16.2.1** The primary objective of the study is to estimate the proportion of complete responders, partial responders or non-responders at 9 months. These proportions will also be estimated at 6 months.

**16.2.2** To determine the time-to-first occurrence of a CR or PR. Subjects who do not achieve CR or PR by the end of the study at 9 months will be considered 'censored for CR (PR)'.

**16.2.3** To catalogue the phenotypic characteristics of the responders and non-responders at 6 and 9 months.

**16.2.4** To examine the frequency and severity of adverse events (AEs) that may arise from the study and to determine if these AEs are related to the study drug.

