# Master Protocol

- a. Complete response (CR): Hb > 9 gm/dL and transfusion-independence as defined in DBA
- b. Partial response (PR): Hb < 9 gm/dL and increased reticulocyte count to greater than 1% and any increase in transfusion interval from baseline. (Baseline reticulocytes range from 0.1 to 0.5 and transfusions are usually performed every 3 weeks. An increase of reticulocyte counts to over 1 to 1.5% and any increase in transfusion interval will be considered a PR.)
- c. No response (NR): no change in transfusion requirements and no significant change in Hb or reticulocytes (or any response that does not satisfy the conditions of either a PR or CR)
- d. Progression: worsening of disease as defined by the need for more frequent transfusions

Secondary outcomes include time-to-occurrence of either a PR or CR, and safety parameters such as type, frequency, and severity of adverse events and relationship to leucine (according to the NCI CTCAE version 4.0).

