## 16.4 Statistical Methods

This is a standard Phase I/II study with the goal of determining the feasibility, safety and efficacy of the use of leucine in transfusion-dependent DBA subjects. A maximum of 50 subjects will be enrolled into the study. The statistical approach will be primarily descriptive in nature.

For specific aim 1, the proportion of subjects achieving a specific response at 6 and 9 months (CR, PR, NR or progression) along with their corresponding 95% confidence intervals, will be calculated using standard methods of estimating proportions.

For specific aim 2, time-to-response (separately for CR and PR) will be analyzed using survival analysis techniques. Subjects who do not achieve CR or PR by the end of the study at 9 months will be considered 'censored for CR (PR)'. Kaplan-Meier curves will be generated and the log-rank test will be used for any comparisons with respect to time-to-CR (PR), if feasible.

For specific aim 3, the approach will be primarily descriptive. However, we may carry out some analyses if feasible. First, response status at 9 months (separately for CR and PR) will be cross-tabulated with certain subject phenotypes; a chi-square test or Fisher's exact test, as appropriate, will be used to determine if there is an association between response status and the certain phenotype. Second, time-to-response will be analyzed. Kaplan-Meier curves will be generated and the log-rank test will be used to compare phenotypes with respect to time-to-CR (PR), if feasible. Subjects who do not achieve CR or PR by the end of the study at 9 months will be considered 'censored for CR (PR)'.

For specific aim 4, the proportion of adverse events will be tabulated and their corresponding 95% confidence interval will be calculated.

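### Sections 14.1.4 and 16.3d define Progression in opposite directions on transfusion interval and differ on volume; a smaller point is that per-transfusion volume is left free while PR counts interval alone

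*Combined protocol and SAP*

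**What the plan says.** Response is defined twice, in section 14.1 and again in section 16.3.

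- **Progression.** Section 14.1.4: "An increased transfusion requirement with increased volume or increased interval". Section 16.3d: "worsening of disease as defined by the need for more frequent transfusions". The second has no volume term.
- **Partial response.** Both versions require Hb below 9 gm/dL, a reticulocyte rise to about 1%, and a transfusion limb. That limb is "any transfusion interval increase" in 14.1.2 and "any increase in transfusion interval from baseline" in 16.3b. Neither mentions volume. Section 16.3b gives the starting point: "Baseline reticulocytes range from 0.1 to 0.5 and transfusions are usually performed every 3 weeks".
- **No response.** Section 16.3c includes a catch-all for anything that meets neither PR nor CR.
- **Use.** Section 16.2.1 states the primary aim as to "estimate the proportion of complete responders, partial responders or non-responders at 9 months". Section 16.4 adds Progression to the categories whose proportions and 95% confidence intervals are calculated at 6 and 9 months.
- **Transfusion on study.** Section 13.2: "Subjects will receive 10-15 ml/kg/transfusion, with all volumes recorded on the Case Report Forms". Section 9.1.2 keeps subjects on their transfusion schedule, and 13.2.1 has those with Hb below 8 and no reticulocyte response transfused in their usual way. Sections 13.2.2 and 13.2.3 allow a hold or, in 13.2.3, a 10 ml/kg transfusion. Section 9.1.1.1 sets entry as a rate, at least 10 cc/kg (or 2 units if over 60 kg) per 28 days averaged over 84 days. It sets no volume per transfusion.

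**The concern.** Lengthening the interval is the sign of benefit that PR counts. Section 14.1.4 names the same change as a route to Progression, while 16.3d names its opposite. On volume, 14.1.4 counts an increase and 16.3d ignores it. An analyst working from section 14 and one working from section 16 can therefore put the same subject in different categories of the primary outcome, and no rule says which section prevails.

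The smaller issue concerns what the interval measures. How long a transfusion lasts depends partly on how much was given. Section 13.2 permits a 1.5-fold range of volume with no link to what the subject received before entry, and interval is PR's only measure of transfusion need. A change in volume can therefore contribute to the transfusion limb.

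**Working it through.** **The plan's own precision figure.** Section 16.5 gives a maximum 95% half-width of 13.9 points at n = 50. Check: 1.96 × √(0.5 × 0.5 / 50) = 0.1386. It reproduces, and nothing here changes it. One subject is 1/50 = 2 points.

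**Classifying example subjects under each section.** The volume and interval pairs are illustrative; the documents give no pre-study distribution. Rate = volume × 28 / interval, in ml/kg per 28 days. Requirement is read as this rate and volume as the amount per transfusion.

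| Change | Rate before → after | Section 14.1 | Section 16.3 |
|---|---|---|---|
| A. 10 ml/kg every 21 days → 15 every 28, with Hb < 9 and reticulocytes above 1% | 10×28/21 = 13.3 → 15×28/28 = 15.0 (+12.5%) | PR (14.1.2) and Progression (14.1.4) | PR |
| B. 10 → 15 ml/kg, interval fixed at 21 days | 13.3 → 15×28/21 = 20.0 | Progression | NR, by the catch-all in 16.3c |
| C. 12 ml/kg, interval 21 → 14 days | 12×28/21 = 16 → 12×28/14 = 24 | Neither named route is met | Progression |
| D. 12 ml/kg, interval 21 → 28 days | 16 → 12×28/28 = 12 | PR's transfusion limb | PR's transfusion limb |

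A shows the overlap, B the volume difference and C the reversed interval. C is Progression under 14.1.4 only if volume is taken to mean total volume over time, which the section does not say. In D the sections agree, because the opening term of 14.1.4 asks for a higher requirement and the requirement has fallen.

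**Volume and the PR transfusion limb.** Assumption: need is constant, so the interval a transfusion supports is proportional to its volume.

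- From 10 ml/kg every 21 days, the volume that supports 28 days is 10 × 28/21 = 13.3 ml/kg. The rate is 13.3 before and after.
- A subject at PR's reticulocyte level already exceeds the 0.5% gate in 13.2.2. A hold then turns on Hb above 8 and clinical stability, and a larger previous transfusion can raise that Hb. A hold at day 21 with a one-week recheck gives at least 28 days.
- A two-week recheck (35 days) would need 10 × 35/21 = 16.7 ml/kg, outside the permitted range.
- Under the 15 ml/kg cap, volume alone can add a full week only from a starting volume of at most 15 × 21/28 = 11.25 ml/kg (3-week baseline) or 15 × 28/35 = 12 ml/kg (4-week baseline).
- Section 13.2 can impose such a change. The entry rate of 10 per 28 days admits 10 × 21/28 = 7.5 ml/kg every 21 days. At the 10 ml/kg minimum, 21 × 10/7.5 = 28 days are supported at the same rate.

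**The case against.** The strongest reply is that 14.1.4 contains a drafting slip. Its opening term is a higher transfusion requirement, 16.3d speaks of more frequent transfusion, and 18.4.4 treats a more frequent need as a serious adverse event. All three show the intended direction. This stands: a reader might infer that the sponsor means a longer interval to count as worsening, and the documents do not support that. But correcting the slip alone would leave subject B in two categories, because the volume terms would still differ.

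On volume, a reader might infer that sites can create partial responses by transfusing more, or that the PR proportion is inflated. The documents do not support that either. PR also needs reticulocytes to rise to about 1% from 0.1 to 0.5, and volume does not supply that rise. A subject with such a rise would be expected to need less transfusion, which sits badly with the constant-need assumption. The reason 13.2.3 gives for its 10 ml/kg option suggests that a larger transfusion may work against a reticulocyte response. Sections 9.1.2 and 13.2.1 also limit drift in practice, although neither expressly fixes a volume. Complete response is unaffected.

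Finally, this is a convenience-sample pilot with mainly descriptive analysis, and no stated decision rule depends on PR. That limits the consequences, but correct description of the response categories is what such a study delivers.

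**Conclusion.** The point holds, chiefly as an inconsistency in the primary outcome. As written, 14.1.4 contradicts 16.3d on interval, its interval term overlaps PR's transfusion limb, and the two sections treat a volume increase differently. Classification can depend on which section is used. Each subject affected moves a proportion by 2 points at n = 50; the number affected cannot be estimated from the documents. It should be fixed before response is classified.

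The volume point is secondary. Volume choice can contribute to PR's transfusion limb, within the narrow conditions worked out above and on the assumption of constant need. It cannot produce a PR without the reticulocyte rise, and it does not justify redefining the endpoint.

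**What to change.** 1. In 14.1.4, change the interval term to a decreased interval (more frequent transfusions), keep the requirement and volume terms, and use identical wording in 16.3d. This costs a few words.
2. In 13.2, keep each subject near the pre-study volume per transfusion, within 10-15 ml/kg, unless clinically required, with the 10 ml/kg option in 13.2.3 as the stated exception.
3. Beside each PR and Progression, report ml/kg per 28 days against the 84-day pre-study value from 9.1.1.1, as a descriptive or sensitivity summary.

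On-study transfusion dates, amounts and weights are already collected, and the pre-study rate is needed for eligibility. The cost of items 2 and 3 is some conversion of units to ml and a little more tabulation. Each 84-day window holds only about 84/28 = 3 to 84/21 = 4 transfusions, so the summary will be coarse.

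I would not make the rate, or a margin on pre-transfusion Hb, a condition of the endpoint. Pre-study Hb beyond the baseline blood count is not listed in section 12, and subjects properly held under 13.2.2 or 13.2.3 could fail such a condition. A rate rule would also label the 7.5 ml/kg subject as Progression if 13.2 raised the volume to 10 ml/kg at an unchanged 21 days (10 to 10 × 28/21 = 13.3 ml/kg per 28 days). For the same reason, a rise imposed only by the 13.2 minimum should not be read as an increased requirement; the summary in item 3 makes such cases visible.
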